If the candidate agrees to be approached, the investigator/research assistant will contact the candidate over the telephone. The topic and the purposes of the study will be introduced. If the candidate is interested, the investigator/research assistant will schedule the visit for recruitment/consent. (Script is followed)

The recruitment/consent visit will be either on the day of the individual's convenience. The investigator/research assistant will provide explanation of the screening, the study procedures involved, the time commitment, and the purpose of written consent. Also, the candidates will be told that phone calls will be made during the study period. Potential subjects will be instructed to read the consent forms carefully. Any questions will be answered before signing. Before written consent is obtained, no personal information will be revealed or recorded. (Pink folder)

After giving informed consent, candidates will first complete the demographic information and 4 self-administered screening tools including the Horne-Ostberg Morningness-Eveningness Questionnaire (MEQ), the International Statistical Classification of Diseases and Related Health Problems (10th revision) (ICD-10) criteria for cancer-related fatigue, Pittsburgh Sleep Quality Index (PSQI), and the Center for Epidemiological Studies Depression Scale (CES-D). A research staff will instruct the participant and administer the Montreal Cognitive Assessment (MoCA) with paper and pencil. After that, candidates will then be individually screened/interviewed for the exclusion criteria (scoring criteria provided). Those who met the study criteria will be scheduled of the study activities (Blue folder).

Participants will be enrolled in the study for approximately 3 weeks. Each participant will make 3 overnight visits to the sleep laboratory. The research protocol consists of a pre-study adaptation night, baseline data collection, 14-day treatment phase, and post-treatment data collection. Night-time Sleep patterns and overnight core body temperature will be monitored in a sleep laboratory before and after the bright light intervention.

	Pre-Study	Baseline		Treatment	Post-Treatment	
Study Day	(prior baseline)	D1	D2	(14 consecutive days)	D1	D2
Bright light protocol				X (daily)		
Polysomnography (overnight only)	Adaptation night	X	End		X	End
Core body temperature (overnight only)	Adaptation night	X	End		X	End

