Self-reported measurement* & cognition assessment		X			X	
Daily log		X	X	X (daily)	X	X

Pre-study adaptation night: To facilitate adaptation to sleep study procedures and a new sleep environment, the participants will report to the sleep laboratory around 8 pm on a convenient weekday. After checking in to the sleep laboratory, the research staff will provide instruction for daily log. A study schedule will be provided to the study participant (completed by a research staff). The sleep lab staff will give a tour to sleep lab. Before going to bed, the person will then be connected to the polysomnography (PSG) recording and undergo continuous PSG for one night. The recorded PSG data during the adaptation night will not be analyzed as per standard sleep research methodology.

The participants will be instructed to complete the 8 self-administered instruments, including PROMIS-Sleep Disturbance, PSQI, PROMIS-Fatigue, PROMIS-depression, CES-D, EORTC

QLQ-C30, PROMIS-Physical Function, and PSS on the day of baseline data collection (blue folder). They will be asked to return the completed instruments on their next sleep lab visit.

Starting from the adaptation night and throughout the study, the participants will complete the daily log each morning and before going to bed to record sleep/wake activities, naptimes, and levels of fatigue throughout the day.

Baseline data collection: Within a week (prefer next day), the participants will return to the sleep laboratory around 7 pm. After checking in the sleep lab), the participants will complete the NIH Toolbox Cognition Battery via iPad Air (administered by the research staff).

The participants will be connected to the PSG recording before going to bed and undergo overnight PSG monitoring. The recording for the PSG analysis will start at the time of lights out and will end at the time of final awakening in the morning (when the individual is out of bed). With the assistant from a research staff, the participant will be instructed to self-insert the thermistor just before going to bed and will remove (by herself) thermistor after final awakening in the morning. Core temperature readings will be continuously monitored and recorded every 5 minutes during the all-night sleep studies. The data at 5 minute intervals starting with lights out will be used for analysis.

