**Effects of Bright Light on Co-occurring Cancer-related Symptoms
in Breast Cancer Survivors**

NCT03304587

PI: [name]

Statistical Analysis Plan

May 1, 2022

Statistical Analysis Plan

The data analysis of **Aim 1** will be descriptive in nature. To assess the feasibility of the proposed study protocol, the numbers of subjects contacted and screened, the proportion of eligible subjects from those contacted, the proportion of those successfully recruited from the pool of eligible subjects, the proportion retained of those recruited, completeness of the data collected, ease of using each measure, and adverse effects (if there are any) will be described using summary statistics. Adherence to treatment will be assessed by measuring timing of visor cap usage. Adherence to outcome reporting will be evaluated by estimating completion rates of scheduled PSG recordings, core body temperature measures, and self-report forms at both time periods. The proportion and the reason for missing data on each outcome will also be assessed.

The objective of **Aim 2** is to assess the effects of bright light on the 4 symptoms (sleep disturbance, fatigue, depression, cognitive dysfunction) and quality of life. Nocturnal sleep patterns will be measured objectively and subjectively. Objective sleep patterns will be monitored in a sleep laboratory by all-night PSG before and after the light intervention. The endpoints for sleep patterns (the sleep continuity measures include sleep onset latency, arousals, wake after sleep onset, and sleep efficiency) will be derived from scoring the PSG record by a polysomnographer blind to intervention assignment. Subjective endpoints for sleep patterns (sleep onset latency, sleep disturbance, and sleep efficiency) will be self-reported by participants before and after the light intervention. For each endpoint, the between-group difference will be compared using two-way ANOVA for repeated measurement data and to account for potential correlation among multiple measurements taken from the same individual. Important covariates such as ambient light and the level of stress (as measured by PSS) will be adjusted if necessary. Fatigue, depression, cognition, and quality of life will be subjectively and objectively assessed before and after the light intervention. Between-group differences in those subjective measurements will be compared using two-way ANOVA.

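### Aim 2 names repeated-measures ANOVA but has no rule for a participant with only one of the two records; a mixed model on all records should be specified, with its missing-data assumption

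*SAP*

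**What the plan says.** **Analysis.** For sleep, SAP Aim 2 states: "For each endpoint, the between-group difference will be compared using two-way ANOVA for repeated measurement data". Fatigue, depression, cognition and quality of life have a separate sentence: "Between-group differences in those subjective measurements will be compared using two-way ANOVA". That sentence does not mention repeated measurement.

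**Missing data.** These appear only under SAP Aim 1, among the feasibility measures. Adherence to outcome reporting will be judged by "estimating completion rates of scheduled PSG recordings, core body temperature measures, and self-report forms at both time periods", and "The proportion and the reason for missing data on each outcome will also be assessed". For Aim 2 there is no complete-case statement, imputation, likelihood method or missing-data assumption.

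**Records per endpoint.** SAP Aim 2 says "Objective sleep patterns will be monitored in a sleep laboratory by all-night PSG before and after the light intervention". The Protocol (Procedures) says "Each participant will make 3 overnight visits to the sleep laboratory". The first of these is the adaptation night, of which the Protocol says "The recorded PSG data during the adaptation night will not be analyzed as per standard sleep research methodology". One baseline night and one post-treatment night remain, and no other night can replace a failed one.

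**The concern.** With two visits, the group-by-time test of classical repeated-measures ANOVA is a two-sample test on within-participant change. A participant with one value has no change score and drops out of that endpoint, although the other value was collected.

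Two things are at stake:

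- **Precision.** The SAP (Aim 3) itself calls the sample relatively small. Under this method it would shrink further, by a different amount for each endpoint.
- **Bias.** If the chance of having both values depends on baseline severity, and does so differently in the two groups, the complete-pair comparison of change is biased. A likelihood model on all records allows for loss that depends on observed values.

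**Working it through.** **Inputs.** The documents state no sample size, alpha, power, standard deviation, correlation or failure rate, so there is no planned figure to reproduce. Assumed here: SD 1; pre-post correlation r = 0.5-0.7; failure probability p = 10-20% per night, independent between nights, or a share d = 10-20% losing only the post-treatment value; two equal groups of N each. N cancels from the ratios in steps 2 to 4.

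**Step 1: who remains.** The share with both records is (1-p)²; with exactly one, 2p(1-p); with none, p².
- p = 0.10: 0.81, 0.18, 0.01
- p = 0.20: 0.64, 0.32, 0.04

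Complete pairs keep 81% or 64% of participants. All records keep 99% or 96%.

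**Step 2: group-by-time contrast, failures on either night.** Let a = (1-p)² be the share with both records and b = p(1-p) the share with one particular record only. Variance of mean change per group:
- complete pairs: 2(1-r)/(N·a)
- all records (generalised least squares): 2/(N·[a/(1-r) + b])

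Ratio = 1 + (1-r)·b/a = 1 + (1-r)·p/(1-p).
- p = 0.10, r = 0.7: 1 + 0.3 × 0.111 = 1.033
- p = 0.20, r = 0.5: 1 + 0.5 × 0.25 = 1.125

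Complete pairs therefore have 3-13% more variance. In standard errors, all records save 1 - 1/√1.033 = 1.6% to 1 - 1/√1.125 = 5.7%.

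**Step 3: same failures, common baseline mean in both analyses.** Variance of the post-treatment group difference: complete pairs 2(1-r²)/(N·a); all records 2/(N·[a/(1-r²) + b]). Ratio = 1 + (1-r²)·p/(1-p).
- p = 0.10, r = 0.7: 1 + 0.51 × 0.111 = 1.057
- p = 0.20, r = 0.5: 1 + 0.75 × 0.25 = 1.188

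This is 6-19% more variance.

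**Step 4: only post-treatment values lost.** Per group, complete pairs 2(1-r)/(N(1-d)); all records (1-r²)/(N(1-d)) + (1-r)²/N. Ratio = 1/(1 - d(1-r)/2).
- d = 0.10, r = 0.7: 1/0.985 = 1.015
- d = 0.20, r = 0.5: 1/0.95 = 1.053

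This is 2-5%. With a common baseline mean there are no post-only records to add, so the ratio is 1.00.

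**Step 5: power.** Simulation (6000 runs; total 40, r = 0.5, 10% failure each night, true difference 0.8 SD, two-sided 5%): 70% with full data, 60% with complete pairs, 62% with the mixed model.

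**Step 6: bias.** Simulation with r = 0.5, no true difference and post-treatment values lost in opposite directions by group; on average 23.4 of 30, 31.2 of 40 and 46.9 of 60 pairs remained. The mixed model was a REML random-intercept fit with a t reference on complete pairs minus 2 degrees of freedom. Entries are bias in SD and type I error.

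| Loss depends on | Total | Complete pairs | Mixed model |
|---|---|---|---|
| observed baseline | 30 | 0.22; 7.9% | 0.00; 5.4% |
| observed baseline | 40 | 0.22; 9.2% | 0.00; 5.6% |
| observed baseline | 60 | 0.22; 11.0% | 0.00; 5.1% |
| unseen post value | 30 | -0.21; 7.4% | -0.32; 11.1% |
| unseen post value | 40 | -0.21; 8.6% | -0.32; 13.7% |
| unseen post value | 60 | -0.21; 11.6% | -0.33; 19.8% |

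**Step 7: complete data and degrees of freedom.** With no missing record, the ANOVA interaction and the unconstrained mixed model gave the same statistic (t = -1.507, p = 0.143). With a default z reference, the mixed model's type I error was 7.2-7.3% at a total of 20, 6.2% at 30 and 5.5-5.6% at 60; a t reference brought it back to about 5%.

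**The case against.** The other side has several good points.

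- **No deletion rule is written.** A reader might infer that the SAP orders incomplete pairs to be dropped. It does not. It speaks of endpoints being "compared using two-way ANOVA for repeated measurement data and to account for potential correlation among multiple measurements taken from the same individual", with no estimation method or software, and that wording does not exclude a likelihood fit. Dropping pairs is the named method's usual behaviour. This stands, and it limits the point to a method that usually discards single records, with no rule to say otherwise.
- **No missing rate is stated.** A reader might infer that the plan expects appreciable loss. The sentence on missing data is a feasibility measure under Aim 1, and the 10-20% used here is an assumption. This stands.
- **The gain in precision is small.** Treatment starts only after baseline data collection is complete (Protocol, Treatment phase), so post-treatment loss is at least as plausible as baseline loss. In that case the gain is 2-5%, or none beyond baseline adjustment. This stands.
- **The bias needs a particular pattern.** Loss must depend on baseline differently by group, and nothing in the documents points to this. Nothing rules it out either, so protection is worth having.
- **Not every outcome is exposed alike.** Participants complete the self-report forms and bring them to the laboratory visit, so a failed recording does not by itself remove them. Thermistor nights belong to Aim 3, outside this ANOVA, and a within-participant phase shift needs both nights under any model.
- **A mixed model is not free.** It relies on missing at random and needs small-sample degrees of freedom, as steps 6 and 7 show. A common baseline mean also presumes random allocation. The documents mention only intervention assignment; their one reference to random selection concerns light-meter days.

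None of this supplies the missing rule for Aim 2.

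**Conclusion.** The point holds in a limited form. The SAP plans to tabulate missing data on each outcome, names a method that in its usual two-visit form sets single records aside, and gives no rule for them. A specified likelihood model is a concrete improvement, worth making before analysis.

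The size is modest and wholly conditional on the assumed failure rates and correlation. The percentages in steps 2 to 4 are the extra variance of complete pairs over all records; they are not a share of lost information recovered. In the simulated case, power rose by only 2 points.

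The stronger reason is bias: about 0.22 SD removed when loss followed the observed baseline in opposite directions by group. That pattern was built into the simulation and is not evidence about this trial.

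A reader might conclude that the mixed model is better whatever the cause of loss. The working does not support that: when loss followed the unseen post-treatment value, the mixed model was more biased than complete pairs in the settings tried. This is why the assumption must be stated and the complete-pair result kept.

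**What to change.** Amend both Aim 2 sentences, the one for sleep endpoints and the one for fatigue, depression, cognition and quality of life, along these lines:

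> Each endpoint will be analysed by a linear mixed model for the baseline and post-treatment values, with unstructured 2x2 covariance, REML and Kenward-Roger degrees of freedom, using every available record. Missing values are assumed missing at random given the observed values and group. The complete-pair analysis will be reported as a sensitivity check.

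Name the contrast as well. If allocation is confirmed as random, fit a common baseline mean and report the post-treatment group difference. Otherwise leave the baseline means free and report the group-by-time contrast. The first choice changes the estimator even when no data are missing; the second reproduces the ANOVA interaction in that case.

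Report the numbers with both, one and no record by group beside each result; the Aim 1 tabulation already collects most of this.

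The cost is a few sentences of SAP text, a standard procedure in place of the ANOVA, and open reliance on missing at random. No extra data are needed. The Aim 3 temperature phase shift is not covered and needs its own statement on incomplete pairs.

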(sleep lab instruction provided, in pink folder) The participants will be asked to refrain from consuming alcohol, using tobacco, and taking over-the-counter sleep or allergy medication during the 12-hour period before checking in to the sleep laboratory and throughout the laboratory session. Snacks (provide to participants at each sleep lab visit) will be available and breakfasts will be provided. The participants are encouraged to bring their personal items, engage in daily activities, e.g., watching TV, reading, etc., and maintain their bedtime ritual during their stay in the sleep laboratory.

Treatment phase: The treatment phase will start on the next day after the completion of baseline data collection. A light visor cap (Physician Engineered Products, Fryeburg, ME) and individualized instruction will be provided upon checking out of the sleep laboratory. A research staff meets with the study participant before checking out. The participants will be instructed to wear the light visor cap with the light on for 30 minutes either within 30 minutes of waking or between 1900-2000 hours for 14 consecutive days. A multiple-alarm watch will be provided (optional). Alarms will be set for on and off times by a research staff. To ensure participant comprehension and ability to perform the personalized light treatment at home, the individual will be asked to demonstrate knowledge of (by verbalizing the time of the day, frequency, and duration of prescribed light treatment) and ability to use (by demonstrating) the light visor cap.

In addition, provide instruction about light meter use. On 2 randomly selected days, one weekday and one weekend day, the subjects will wear a light meter during wake time, starting from rising in the morning and ending at bedtime in the evening. To enhance adherence to the use of the light meter, participants will receive a phone reminder the day before.

Throughout the 14-day treatment phase, the participants will continue completing the daily log each morning and before going to bed. In addition, they will be instructed to record the time of

the beginning and the end of each light treatment on the daily log. Participants will receive a daily phone call from a research staff member for the first 1-3 days and then weekly phone calls for the rest of the treatment phase.

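### Aim 2 does not name the ANOVA term that is the treatment effect; if assignment is random, adjusting for the outcome's own baseline would usually give more precision from data already collected (minor)

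*SAP*

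**What the plan says.** The Aim 2 paragraph of the SAP has two analysis sentences. For objective and subjective sleep endpoints, "the between-group difference will be compared using two-way ANOVA for repeated measurement data", with allowance for within-person correlation. For fatigue, depression, cognition and quality of life, "Between-group differences in those subjective measurements will be compared using two-way ANOVA"; here the repeated-measures structure is not mentioned. Neither sentence says whether the group main effect or the group-by-time interaction is the treatment effect.

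On covariates: "Important covariates such as ambient light and the level of stress (as measured by PSS) will be adjusted if necessary". The outcome's own baseline value is not named.

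The pre-treatment values exist. Under the Protocol's pre-study and baseline headings, participants complete "8 self-administered instruments, including PROMIS-Sleep Disturbance, PSQI, PROMIS-Fatigue, PROMIS-depression, CES-D, EORTC" QLQ-C30, PROMIS-Physical Function, "and PSS on the day of baseline data collection". The NIH Toolbox and overnight PSG are also done at the baseline visit. All of these are repeated after treatment. PSQI and CES-D are given at screening as well. MoCA is given at screening and after treatment, but is not listed for the baseline visit.

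On groups, the Protocol's treatment phase describes wearing the visor "for 30 minutes either within 30 minutes of waking or between 1900-2000 hours for 14 consecutive days". The SAP has PSG scored "by a polysomnographer blind to intervention assignment". Neither document says how assignment is made, and neither gives a sample size, an SD or a pre/post correlation.

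**The concern.** Two things are left open. First, a two-way group-by-time ANOVA contains a group term, a time term and their interaction. A between-group difference most naturally means the interaction here, but the words do not settle it. Two analysts could in principle report different quantities.

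Second, when groups are formed at random, the change score is not usually the most efficient use of a baseline measurement. It subtracts the whole baseline value, whereas ANCOVA subtracts only as much as the data support. The SAP describes its own sample as relatively small, so precision matters, and the values needed are already being collected. What is at stake is the width of the Aim 2 confidence intervals, not the validity of the comparison.

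**Working it through.** **Inputs.** From the documents: two light timings; endpoints measured before and after treatment; two-way ANOVA. There is no stated power or precision figure to reproduce. Assumed: 1:1 random assignment, n per arm with N = 2n, n from 10 to 30, pre/post correlation ρ from 0.3 to 0.9, and baseline SD 1. The post-treatment SD is k, with k = 1 unless stated.

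**Step 1: what each term estimates.** Let the treatment effect be δ, with no effect at baseline.
- Group-by-time: difference in post minus difference in pre = δ. This is the change-score comparison.
- Group main effect: average of the pre and post differences = (0 + δ)/2. A true 0.80 SD would be estimated as 0.40 SD.

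**Step 2: variances with equal SDs.**
- Change score: (2/n) × 2(1 − ρ).
- ANCOVA: (2/n) × (1 − ρ²) × (N − 3)/(N − 4). The last factor is the expected cost of chance baseline imbalance.
- Ratio, ANCOVA to change: ((1 + ρ)/2) × (N − 3)/(N − 4).

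Example, n = 20 and ρ = 0.5: 0.75 × 37/36 = 0.77.

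| n per arm | ρ = 0.3 | 0.5 | 0.7 | 0.8 | 0.9 |
|---|---|---|---|---|---|
| 10 | 0.69 | 0.80 | 0.90 | 0.96 | 1.01 |
| 20 | 0.67 | 0.77 | 0.87 | 0.93 | 0.98 |
| 30 | 0.66 | 0.76 | 0.87 | 0.92 | 0.97 |

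Simulation with 20,000 trials per setting agrees to within 0.01. In it the 95% CI is 11–13% narrower at ρ = 0.5 (n = 20: half-width 0.558 against 0.636 SD). At ρ = 0.9 it runs from 1% wider (n = 10) to 2% narrower (n = 30). Type I error is 4.8–5.2% for both methods.

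**Step 3: break-even with equal SDs.** Setting the ratio to 1 gives ρ = (N − 5)/(N − 3).
- N = 20: 15/17 = 0.88. N = 30: 25/27 = 0.93. N = 40: 35/37 = 0.95. N = 60: 55/57 = 0.96.
- N = 10: 5/7 = 0.71. N = 12: 7/9 = 0.78.

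**Step 4: unequal SDs.** Change-score variance is (2/n)(1 + k² − 2ρk); ANCOVA variance is (2/n)k²(1 − ρ²)(N − 3)/(N − 4). Take k = 1.2.
- At ρ = 0.5: 1.08/1.24 = 0.87. Times 17/16 (n = 10) this is 0.93; times 57/56 (n = 30) it is 0.89. The gain shrinks to 7–11%.
- Break-even at n = 10: 1.53ρ² − 2.4ρ + 0.91 = 0, so ρ = (2.4 − 0.437)/3.06 = 0.64. The same steps give 0.69 at n = 15 and 0.72 at n = 20. The quadratic has a second root (0.93 at n = 10), above which ANCOVA leads again.

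**Step 5: the most ANCOVA can lose.** In large samples ANCOVA never has the larger variance, because the change score is the special case with slope fixed at 1. So the ratio cannot exceed (N − 3)/(N − 4): 17/16 = 1.06 at n = 10 and 37/36 = 1.03 at n = 20.

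**Step 6: if assignment is not random.** With a stable baseline gap g and no treatment effect, ANCOVA has expectation g − ρg = (1 − ρ)g, while the change score has expectation 0. For an assumed gap of 0.5 SD that is 0.35 SD at ρ = 0.3 and 0.05 SD at ρ = 0.9.

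**The case against.** The strongest reply is that the planned analysis is already sound. In a repeated-measures ANOVA on pre and post values, baseline is one of the two responses; not entering it again as a covariate is how the model works. That stands: this is a choice between valid estimators. The wording on covariates is also open-ended, so baseline is not excluded, although it is not prespecified.

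A reader might infer that Aim 2 will report half the true effect. The documents do not support this. The SAP speaks of effects of bright light measured before and after, by repeated-measures ANOVA, and group-by-time is the natural reading. The halving shows why the term should be named, but it should not set the severity.

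A reader might also infer that ANCOVA wins at any correlation below about 0.9. That depends on a sample size and an SD ratio that the documents do not give. The threshold falls to 0.71–0.78 at a total N of 10–12, and to 0.64–0.72 at 10–20 per arm if the post-treatment SD is 1.2 times the baseline SD. An SD ratio below 1 would favour ANCOVA.

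Finally, the benefit requires random assignment, which is not stated, and the SAP's remark on estimation and precision concerns the mediation analysis, not Aim 2. Both points stand, and the fix is conditional for that reason.

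**Conclusion.** The point holds as a minor one. The SAP leaves the treatment-effect term unnamed and does not prespecify adjustment for the outcome's own baseline. On the natural reading nothing is biased.

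If assignment is random, SDs are equal and there are 10–30 per arm, ANCOVA cuts the variance by about 20–24% at ρ = 0.5 and by 4–8% at ρ = 0.8, with little or nothing gained at 0.9. Break-even is 0.88–0.96 under those assumptions and lower with fewer participants or a larger post-treatment SD. With 10 or more per arm the loss beyond break-even is at most about 6% in variance. All sizes are assumption-based. If assignment is not random, only the clarification remains.

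**What to change.** First state in the SAP how participants are assigned to the light timings.

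If at random, replace both ANOVA sentences with:

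> For every Aim 2 endpoint measured before and after treatment, the treatment effect is the between-group difference in the post-treatment value adjusted for the pre-treatment value of the same endpoint (ANCOVA), with a 95% CI. The pre-treatment value is the baseline-visit value (including PSQI and CES-D), except MoCA, if analysed, for which it is the screening value. The group main effect is not interpreted.

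If not at random, keep the repeated-measures ANOVA for all Aim 2 endpoints, including fatigue, depression, cognition and quality of life. Name the group-by-time contrast as the treatment effect, accounting for within-person correlation, with a 95% CI.

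The cost is SAP wording; no new data are needed. ANCOVA uses one degree of freedom per endpoint and loses a little precision if the correlation lies above break-even.

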The participants will be instructed to complete the 8 self-administered instruments, including PROMIS-Sleep Disturbance, PSQI, PROMIS-Fatigue, PROMIS-depression, CES-D, EORTC QLQ-C30, PROMIS-Physical Function, and PSS on the day of posttest data collection. They will be asked to return the completed instruments on their sleep lab visit.

Post-treatment data collection: The post-treatment data collection will start on the next day after completion of the 14-day intervention protocol. Following the same protocol described in baseline data collection, the participants will report to the sleep laboratory 7 pm and then complete the MoCA and the NIH Toolbox Cognition Battery, administered by a research staff.

Before going to bed, the participants will be connected to the PSG recording at their regular bedtime hours and undergo overnight PSG monitoring. With the assistant from a research staff, the participant will self-insert the thermistor just before going to bed and will remove thermistor after final awakening in the morning. The PSG and core temperature recordings for the analysis will start at the time of lights out and will end after final awakening in the morning. During the post-treatment data collection, the participants will complete the daily log before going to bed and the following morning.

Before checking out of the sleep laboratory, the participant will return the daily log. All participants will receive an exit interview before checking out the sleep lab or within 3 days regarding issues or difficulties encountered during the study and complete a list of rating scales measuring levels of burden for study activities.

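### PSQI and CES-D are each scored twice before light, but the Aim 2 before/after ANOVA gives the screening score no role and uses neither pre-light score as a covariate

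*SAP*

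**What the plan says.** **First pre-light score.** In the protocol's Procedures section, candidates complete four self-administered screening tools after consent, among them "Pittsburgh Sleep Quality Index (PSQI), and the Center for Epidemiological Studies Depression Scale (CES-D". The result feeds eligibility: "Those who met the study criteria will be scheduled of the study activities". No cut-off for either scale is given.

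**Second pre-light score.** Under the pre-study adaptation night, participants are told to complete eight forms, including "PROMIS-Sleep Disturbance, PSQI, PROMIS-Fatigue, PROMIS-depression, CES-D, EORTC", with the rest of the list running to "QLQ-C30, PROMIS-Physical Function, and PSS on the day of baseline data collection (blue folder".

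**Post-light score.** Under the treatment phase, the same eight forms are completed again: "QLQ-C30, PROMIS-Physical Function, and PSS on the day of posttest data collection".

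**Analysis.** In the SAP under Aim 2, subjective sleep is self-reported before and after the intervention and compared by two-way ANOVA for repeated measurements. For the other domains the SAP says "Fatigue, depression, cognition, and quality of life will be subjectively and objectively assessed before and after the light intervention" and again names two-way ANOVA. Ambient light and stress may be adjusted for if necessary; pre-light values of the outcome are not mentioned as covariates. Aim 1 speaks of two time periods for the self-report forms, and the protocol's schedule table marks self-report only at Baseline D1 and Post-Treatment D1.

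**The concern.** Each enrolled participant should have two pre-light scores and one post-light score on a sleep scale and a depression scale. The natural reading of the SAP is a two-occasion comparison. In that analysis the group-by-time term is simply the between-group difference in mean change from one before value. This leaves two things unused. The change score fixes the slope on the before value at 1 instead of estimating it, which costs precision whenever the correlation is below 1. The screening score, which may carry further information on the participant's usual level, does not enter at all.

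The SAP itself calls the sample relatively small, so precision matters. In addition, because two pre-light scores exist and neither is named as the before value, that choice could be made after the data are seen.

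**Working it through.** **No plan figure to reproduce.** The documents give no sample size, SD, correlation, screening-to-baseline interval or eligibility cut-off. Everything below rests on assumptions: correlation ρ of 0.5 to 0.7 between adjacent occasions, total N of 20 to 60 in two equal groups, and allocation unrelated to the pre-light scores. The two-way ANOVA is taken as repeated-measures for both scales.

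**Residual variances**, in units of the variance of one score:
- Planned ANOVA (change from one before value): 2(1−ρ).
- ANCOVA on the baseline-day score: 1−ρ².
- ANCOVA on both pre-light scores, equal correlations: 1−2ρ²/(1+ρ).
- ANCOVA on both, when correlation decays with time (screening-to-post correlation ρ²): 1−ρ². The screening score then adds nothing.

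**Cost of covariates.** With k covariates, chance imbalance between groups inflates the variance of the group effect by (N−3)/(N−3−k) on average. For N = 20 this is 17/16 with one covariate and 17/15 with two. For N = 60 it is 57/56 and 57/55.

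| Correlation pattern | Change | ANCOVA, baseline day | ANCOVA, both | SE cut, both v change (N=20 / 60) | SE cut, baseline day only v change (N=20 / 60) | SE cut from adding screening (N=20 / 60) |
|---|---|---|---|---|---|---|
| Equal, ρ=0.5 | 1.000 | 0.750 | 0.667 | 13% / 17% | 11% / 13% | 3% / 5% |
| Equal, ρ=0.7 | 0.600 | 0.510 | 0.424 | 11% / 14% | 5% / 7% | 6% / 8% |
| Decaying, ρ=0.5 | 1.000 | 0.750 | 0.750 | 8% / 12% | 11% / 13% | −3% / −1% |
| Decaying, ρ=0.7 | 0.600 | 0.510 | 0.510 | 2% / 6% | 5% / 7% | −3% / −1% |

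Worked example, equal ρ=0.5, N=60: 0.667 × 57/55 = 0.691; √(0.691/1.000) = 0.831, a 17% cut. Ignoring the degree-of-freedom cost, √0.667 = 0.816, an 18% cut, which is the upper limit.

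**Selection on the screening score.** Suppose only those above the mean, or above 0.5 SD, are enrolled.
- With equal correlations, the screening score's reduction in ANCOVA variance falls from 11% to 4–5% at ρ=0.5, and from 17% to 8–10% at ρ=0.7.
- With decaying correlation, ρ=0.7 and a cut at the mean, the covariance of change with screening is 0.49−0.70 = −0.21. The screening variance shrinks by 2/π = 0.637, so the change variance becomes 0.600−0.21²×0.637 = 0.572. The two-covariate ANCOVA at N=20 gives 0.510×17/15 = 0.578. √(0.578/0.572) = 1.005, so the two analyses are about equal. This is the 0% end of the range.

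**Why not add the screening score to the ANOVA.** In the repeated-measures model the baseline-day score is an outcome. A subject-level covariate entered as a main effect shifts both occasions equally and cancels out of the group-by-time contrast. The model itself has to change.

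**Why not average the two pre-light scores.** With equal correlations the change variance goes from 2(1−ρ) to 1.5(1−ρ), and 1−√0.75 = 13% off the SE. With decaying correlation it is 1.5−0.5ρ−ρ². At ρ=0.5 that is 1.00 against 1.00, no gain; at ρ=0.7 it is 0.66 against 0.60, a 10% increase in variance.

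**The case against.** A reader might infer that the SAP discards the screening scores and with them free precision. The text does not go that far. It never says that exactly one before value is used, and repeated-measures ANOVA could take three occasions. It does not name the PSQI or CES-D either: the PROMIS sleep and depression forms, which have no screening value, could be the intended endpoints. What stands is narrower. The before/after wording, the two time periods in Aim 1 and the schedule table all point to two occasions, and no role for the screening score is written down.

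Nor is the precision free. These are screening tools. If their scores decide eligibility, the screening score is truncated and subject to regression to the mean, in a direction the documents do not reveal. The 13% figure is tempting, but it belongs to averaging under equal correlations. It is not the gain from the covariate approach, and averaging can lose precision. Averaging only when the two means look alike would also be a data-dependent rule.

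The opposing case is also right that much of the benefit is available from the baseline-day score alone, that a further covariate can cost more than it returns in a very small sample, and that replacing the ANOVA is more than a one-line insertion. These points reduce the size of the gain. They do not remove the case for prespecifying how the available pre-light scores are used.

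**Conclusion.** The point holds as a minor matter of precision and clarity. For PSQI and CES-D, an ANCOVA on both pre-light scores lowers the standard error by about 0% to 18% against the planned before/after ANOVA, under assumed correlations of 0.5 to 0.7 and N of 20 to 60. Most of this comes from baseline adjustment in most of the settings; with equal correlations of 0.7 and no selection the two shares are about even. The screening score's own part, about −3% to +8%, depends on N, on selection at screening and on how fast the correlation decays, none of which the documents state.

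A reader should not infer that the planned analysis is biased or invalid. Using the baseline-day score alone would be valid and unbiased, and it matches the schedule table.

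**What to change.** In the SAP under Aim 2, for PSQI and CES-D:
- name the baseline-day score as the before value;
- replace the before/after ANOVA with an ANCOVA of the post-treatment score on group, with the baseline-day score and the screening score as prespecified covariates;
- do not average the two pre-light scores conditionally on how similar their means are.

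No new data, visits or forms are needed. The cost is a changed model for two scales and one extra degree of freedom for the screening term, which can cancel that term's own contribution in a very small sample. If the planned N is near the bottom of the range used here, the sponsor could reasonably prespecify the baseline-day score as the only covariate and say so. Either choice should be fixed before the outcome data are examined.
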